#### **8.1.3 Type 1 diabetes mellitus (if new onset, including diabetic ketoacidosis [DKA]) or ≥ Grade 3 Hyperglycemia, if associated with ketosis (ketonuria) or metabolic acidosis (DKA)**

- For T1DM or Grade 3-4 Hyperglycemia
- Insulin replacement therapy is recommended for Type I diabetes mellitus and for Grade 3-4 hyperglycemia associated with metabolic acidosis or ketonuria.
- Evaluate patients with serum glucose and a metabolic panel, urine ketones, glycosylated hemoglobin, and C-peptide.

#### **8.1.4 Hypophysitis:**

- For Grade 2 events, treat with corticosteroids. When symptoms improve to Grade 1 or less, steroid taper should be started and continued over no less than 4 weeks. Replacement of appropriate hormones may be required as the steroid dose is tapered.
- For Grade 3-4 events, treat with an initial dose of IV corticosteroids followed by oral corticosteroids. When symptoms improve to Grade 1 or less, steroid

taper should be started and continued over no less than 4 weeks. Replacement of appropriate hormones may be required as the steroid dose is tapered.

### 8.1.5 Hyperthyroidism or Hypothyroidism:

Thyroid disorders can occur at any time during treatment. Monitor patients for changes in thyroid function (at the start of treatment, periodically during treatment, and as indicated based on clinical evaluation) and for clinical signs and symptoms of thyroid disorders.

- Grade 2 hyperthyroidism events (and Grade 2-4 hypothyroidism):
- In hyperthyroidism, non-selective beta-blockers (e.g. propranolol) are suggested as initial therapy.
- In hypothyroidism, thyroid hormone replacement therapy, with levothyroxine or liothyronine, is indicated per standard of care.
- Grade 3-4 hyperthyroidism
- Treat with an initial dose of IV corticosteroid followed by oral corticosteroids. When symptoms improve to Grade 1 or less, steroid taper should be started and continued over no less than 4 weeks. Replacement of appropriate hormones may be required as the steroid dose is tapered.

### 8.1.6 Hepatic:

- For Grade 2 events, monitor liver function tests more frequently until returned to baseline values (consider weekly).
- Treat with IV or oral corticosteroids
- For Grade 3-4 events, treat with intravenous corticosteroids for 24 to 48 hours.
- When symptoms improve to Grade 1 or less, a steroid taper should be started and continued over no less than 4 weeks.

### 8.1.7 Renal Failure or Nephritis:

- For Grade 2 events, treat with corticosteroids.
- For Grade 3-4 events, treat with systemic corticosteroids.
- When symptoms improve to Grade 1 or less, steroid taper should be started and continued over no less than 4 weeks.

### 8.1.8 Management of Infusion Reactions: Signs and symptoms usually develop during or shortly after drug infusion and generally resolve completely within 24 hours of completion of infusion.

Table 3 below shows treatment guidelines for subjects who experience an infusion reaction associated with administration of pembrolizumab (MK-3475).

**Table 3 Infusion Reaction Treatment Guidelines**

NCI CTCAE Grade	Treatment	Premedication at subsequent dosing
Grade 1 Mild reaction; infusion interruption not indicated; intervention not indicated	Increase monitoring of vital signs as medically indicated until the subject is deemed medically stable in the opinion of the investigator.	None
Grade 2 Requires infusion interruption but responds promptly to symptomatic	Stop Infusion and monitor symptoms.	Subject may be premedicated 1.5h ( $\pm$ 30 minutes) prior to infusion

NCI CTCAE Grade	Treatment	Premedication at subsequent dosing

treatment (e.g., antihistamines, NSAIDS, narcotics, IV fluids); prophylactic medications indicated for < =24 hrs
	
Additional appropriate medical therapy may include but is not limited to:
 
 
IV fluids
 
Antihistamines
 
NSAIDS
 
Acetaminophen
 
Narcotics
 
 
Increase monitoring of vital signs as medically indicated until the subject is deemed medically stable in the opinion of the investigator.
 
If symptoms resolve within one hour of stopping drug infusion, the infusion may be restarted at 50% of the original infusion rate (e.g., from 100 mL/hr to 50 mL/hr). Otherwise dosing will be held until symptoms resolve and the subject should be premedicated for the next scheduled dose.
 
Subjects who develop Grade 2 toxicity despite adequate premedication should be permanently discontinued from further trial treatment administration.
	
of pembrolizumab (MK-3475) with:
 
Diphenhydramine 50 mg po (or equivalent dose of antihistamine).
 
Acetaminophen 500-1000 mg po (or equivalent dose of antipyretic).


Grades 3 or 4 Grade 3: Prolonged (i.e., not rapidly responsive to symptomatic medication and/or brief interruption of infusion); recurrence of symptoms following initial improvement; hospitalization indicated for other clinical sequelae (e.g., renal impairment, pulmonary infiltrates) Grade 4: Life-threatening; pressor or ventilatory support indicated
	
Stop Infusion. Additional appropriate medical therapy may include but is not limited to:
 
 
IV fluids
 
Antihistamines
 
NSAIDS
 
Acetaminophen
 
Narcotics
 
Oxygen
 
Pressors
 
Corticosteroids
 
Epinephrine
 
 
Increase monitoring of vital signs as medically indicated until the subject is deemed medically stable in the opinion of the investigator. Hospitalization may be indicated.
	
No subsequent dosing

NCI CTCAE Grade	Treatment	Premedication at subsequent dosing
	Subject is permanently discontinued from further trial treatment administration.	
Appropriate resuscitation equipment should be available in the room and a physician readily available during the period of drug administration.		

### 8.1.9 Management of Stevens-Johnson syndrome and Toxic Epidermal Necrolysis:

To date, approximately 11,000 patients in clinical trials and 27,000 patients in the post-marketing setting have been treated with pembrolizumab (MK-3475). One fatal case of SJS in a clinical trial and one fatal case of TEN in the post-marketing setting have been reported in patients treated with pembrolizumab (MK-3475). Including these cases, there have been 8 cases of SJS (6 in clinical trials, and 2 post-marketing) and 2 cases of TEN (both post-marketing) all of which were serious.

- For signs or symptoms of SJS or TEN, withhold pembrolizumab (MK-3475) and refer the patient for specialized care for assessment and treatment.
- If SJS or TEN is confirmed, permanently discontinue pembrolizumab (MK-3475).

### 8.1.10 Management of Immune-mediated myocarditis:

A total of 6 cases of myocarditis have been reported in patients treated with pembrolizumab (MK-3475) in clinical trials or in an expanded access program. There was 1 fatal case reported in a clinical trial.

- For suspected immune-mediated myocarditis, ensure adequate evaluation to exclude other etiologies, and administer corticosteroids as appropriate.

## 8.2 Dose Modifications

The dose of pembrolizumab (MK-3475) is not modified. Doses may be delayed or held as above.

## 9.0 ADVERSE EVENTS

The prompt reporting of adverse events is the responsibility of each investigator engaged in clinical research, as required by Federal Regulations. Adverse events must be described and graded using the terminology and grading categories defined in the NCI's Common Terminology Criteria for Adverse Events (CTCAE), Version 5.0. The CTCAE is available at [ctep.cancer.gov/protocolDevelopment/electronic\\_applications/ctc.htm](http://ctep.cancer.gov/protocolDevelopment/electronic_applications/ctc.htm). Attribution to protocol treatment for each adverse event must be determined by the investigator and reported on the required forms. Please refer the NCI Guidelines: Adverse Event Reporting Requirements for further details on AE reporting procedures.

### 9.1 Routine Adverse Event Reporting

Adverse event data collection and reporting, which are required as part of every clinical trial are done to ensure the safety of patients enrolled in the studies as well as those who will enroll in future studies using similar agents. Adverse events are reported in a routine manner at scheduled times according to the study calendar in [Section 5.0](#). For this trial, the form "Adverse Events" is used for routine AE reporting in Rave.

This trial will be utilizing the Rave-CTEP-AERS integration. All routine, post-baseline adverse events reported in Rave will be evaluated for expedited reporting using protocol-specific rules. If an expedited report is recommended, a deep-link within Rave can be used to automatically launch and log-in to CTEP-AERS to complete the expedited report. Adverse event data in Rave that is required for expedited reporting will be pushed to CTEP-AERS.

Note: Modifications to AE data must begin in Rave since it is the data source. Any adverse event data modified in Rave must be re-submitted for rule evaluation and will then be pushed to CTEP-AERS.

**Solicited Adverse Events:** The following adverse events are considered "expected" and their presence/absence should be solicited, and severity graded, at baseline and for each cycle of treatment by CTCAE.

CTCAE v5.0 Term	CTCAE v5.0 System Organ Class (SOC)
Hyperthyroidism	Endocrine disorders
Hypothyroidism	Endocrine disorders
Headache	Nervous system disorders
Blurred Vision	Eye disorders
Agitation	Psychiatric disorders
Libido decreased	Psychiatric disorders
Personality change	Psychiatric disorders
Diarrhea	Gastrointestinal disorders
Colitis	Gastrointestinal disorders
Abdominal Pain	Gastrointestinal disorders
Pruritus	Skin and subcutaneous tissue disorders
Rash maculo-papular	Skin and subcutaneous tissue disorders
Bullous dermatitis	Skin and subcutaneous tissue disorders
Mucositis oral	Gastrointestinal disorders
Bruising	Injury, poisoning and procedural complications
Generalized muscle weakness	Musculoskeletal and connective tissue disorders
Peripheral sensory neuropathy	Nervous system disorders
Dyspnea	Respiratory, thoracic and mediastinal disorders

## 9.2 CTCAE Routine Reporting Requirements

In addition to the solicited adverse events listed in Section 9.1, the following table outlines the combinations of time points, grades and attributions of AEs that require routine reporting to the Alliance Statistics and Data Center. Questions about routine reporting should be directed to the Data Manager.

Combinations of CTCAE Grade & Attribution Required for Routine AE Data Submission on Case Report Forms (CRFs)

Attribution	Grade 1	Grade 2	Grade 3	Grade 4	Grade 5
Unrelated			a	a	a
Unlikely			a	a	a
Possible	a	a	a, b	a, b	a, b
Probable	a	a	a, b	a, b	a, b
Definite	a	a	a, b	a, b	a, b

- a) Adverse Events: Other CRF - Applies to AEs occurring between registration and within 30 days of the patient's last treatment date, or as part of the Clinical Follow-Up Phase.
- b) Adverse Events: Late CRF - Applies to AEs occurring greater than 30 days after the patient's last treatment date.

## 9.3 Expedited Adverse Event Reporting (CTEP-AERS)

Investigators are required by Federal Regulations to report serious adverse events as defined in the table below. Alliance investigators are required to notify the Alliance Central Protocol Operations Program, the Study Chair, and their Institutional Review Board if a patient has a reportable serious adverse event. The descriptions and grading scales found in the NCI Common Terminology Criteria for Adverse Events (CTCAE) version 5 will be utilized for AE reporting. The CTCAE is identified and located on the CTEP website at: [ctep.cancer.gov/protocolDevelopment/electronic\\_applications/ctc.htm](https://ctep.cancer.gov/protocolDevelopment/electronic_applications/ctc.htm). All appropriate treatment areas should have access to a copy of the CTCAE. All reactions must first be reported in Rave on the "Adverse Events" Form and sent for rule evaluation at the time the event is known. Adverse event data should not be entered in CTEP-AERS prior to entry in Rave for rules evaluation. Additional information about Rave-CTEP-AERS is available on the CTSU website (<https://www.ctsu.org>) under the "Resources" tab.

In the rare occurrence when Internet connectivity is lost, a 24-hour notification is to be made to CTEP by telephone at [contact]. Once Internet connectivity is restored, the 24-hour notification phoned in must be entered electronically into CTEP-AERS by the original submitter at the site.

For further information on the NCI requirements for SAE reporting, please refer to the 'NCI Guidelines for Investigators: Adverse Event Reporting Requirements' document published by the NCI.

Note: All deaths on study require both routine and expedited reporting regardless of causality. Attribution to treatment or other cause should be provided.

### 9.3.1 Late Phase 2 and Phase 3 Studies: Expedited Reporting Requirements for Adverse Events that Occur on Studies under an IND/IDE within 30 Days of the Last Administration of the Investigational Agent/Intervention

#### FDA REPORTING REQUIREMENTS FOR SERIOUS ADVERSE EVENTS (21 CFR Part 312)

**NOTE:** Investigators **MUST** immediately report to the sponsor (NCI) **ANY** Serious Adverse Events, whether or not they are considered related to the investigational agent(s)/intervention (21 CFR 312.64)

An adverse event is considered serious if it results in **ANY** of the following outcomes:

- 1) Death
- 2) A life-threatening adverse event
- 3) An adverse event that results in inpatient hospitalization or prolongation of existing hospitalization for  $\geq$  24 hours
- 4) A persistent or significant incapacity or substantial disruption of the ability to conduct normal life functions
- 5) A congenital anomaly/birth defect.
- 6) Important Medical Events (IME) that may not result in death, be life threatening, or require hospitalization may be considered serious when, based upon medical judgment, they may jeopardize the patient or subject and may require medical or surgical intervention to prevent one of the outcomes listed in this definition. (FDA, 21 CFR 312.32; ICH E2A and ICH E6).

**ALL SERIOUS** adverse events that meet the above criteria **MUST** be immediately reported to the NCI via electronic submission within the timeframes detailed in the table below.

Hospitalization	Grade 1 Timeframes	Grade 2 Timeframes	Grade 3 Timeframes	Grade 4 & 5 Timeframes
Resulting in Hospitalization $\geq$ 24 hrs	10 Calendar Days			24-Hour 5 Calendar Days
Not resulting in Hospitalization $\geq$ 24 hrs	Not required	10 Calendar Days		

**NOTE:** Protocol specific exceptions to expedited reporting of serious adverse events are found in the Specific Protocol Exceptions to Expedited Reporting (SPEER) portion of the CAEPR

#### **Expedited AE reporting timelines are defined as:**

- “24-Hour; 5 Calendar Days” - The AE must initially be submitted electronically within 24 hours of learning of the AE, followed by a complete expedited report within 5 calendar days of the initial 24-hour report.
- “10 Calendar Days” - A complete expedited report on the AE must be submitted electronically within 10 calendar days of learning of the AE.

Serious adverse events that occur more than 30 days after the last administration of investigational agent/intervention and have an attribution of possible, probable, or definite require reporting as follows:

#### **Expedited 24-hour notification followed by complete report within 5 calendar days for:**

- All Grade 4, and Grade 5 AEs

#### **Expedited 10 calendar day reports for:**

- Grade 2 adverse events resulting in hospitalization or prolongation of hospitalization
- Grade 3 adverse events

For studies using PET or SPECT IND agents, the AE reporting period is limited to 10 radioactive half-lives, rounded UP to the nearest whole day, after the agent/intervention was last administered. Footnote “1” above applies after this reporting period.

Effective Date: May 5, 2011

### 9.3.2 Expedited AE reporting timelines defined

“24 hours; 5 calendar days” – The investigator must initially report the AE via CTEP-AERS  $\leq$  24 hours of learning of the event followed by a complete CTEP-AERS report  $\leq$  5 calendar days of the initial 24-hour report.

“10 calendar days” - A complete CTEP-AERS report on the AE must be submitted  $\leq$  10 calendar days of the investigator learning of the event.

Any medical event equivalent to CTCAE grade 3, 4, or 5 that precipitates hospitalization (or prolongation of existing hospitalization) must be reported regardless of attribution and designation as expected or unexpected with the exception of any events identified as protocol-specific expedited adverse event reporting exclusions (see below).

Any event that results in persistent or significant disabilities/incapacities, congenital anomalies, or birth defects must be reported via CTEP-AERS if the event occurs following treatment with an agent under a CTEP IND.

Use the NCI protocol number and the protocol-specific patient ID provided during trial registration on all reports.

### 9.3.3 Additional Instructions or Exclusion to CTEP-AERS Expedited Reporting Requirements for Phase 2 and 3 Trials Utilizing an Agent Under a CTEP IND or non-CTEP IND

- All adverse events reported via CTEP-AERS (i.e., serious adverse events) should also be forwarded to your local IRB.
- Alliance A091605 uses a drug under a CTEP IND. The reporting requirements for investigational agents under a CTEP IND should be followed for all agents (any arm) in this trial.
- Death due to progressive disease should be reported as Grade 5 “Disease progression” in the system organ class (SOC) “General disorders and administration site conditions.” Evidence that the death was a manifestation of underlying disease (e.g., radiological changes suggesting tumor growth or progression: clinical deterioration associated with a disease process) should be submitted.
- Any death occurring within 30 days of the last dose, regardless of attribution to the investigational agent/intervention requires expedited reporting within 24 hours.
- Any death occurring greater than 30 days after the last dose of the investigational agent/intervention requires expedited reporting within 24 hours only if it is possibly, probably, or definitely related to the investigational agent/intervention.
- All new malignancies must be reported via CTEP-AERS whether or not they are thought to be related to either previous or current treatment. All new malignancies should be reported, i.e. solid tumors (including non-melanoma skin malignancies), hematologic malignancies, myelodysplastic syndrome/acute myelogenous leukemia, and in situ tumors. In CTCAE version 5.0, the events may be reported as either: (1) Leukemia secondary to oncology chemotherapy, (2) Myelodysplastic syndrome, or (3) Treatment-related secondary malignancy. Whenever possible, the CTEP-AERS reports for new malignancies should include tumor pathology, history or prior tumors, prior treatment/current treatment including duration, any associated risk factors or evidence regarding how long the new malignancy may have been present, when and how the new malignancy was detected, molecular characterization or cytogenetics of

the original tumor (if available) and of any new tumor, and new malignancy treatment and outcome, if available.

- Any malignancy possibly related to cancer treatment (including AML/MDS) should also be reported via the routine reporting mechanisms outlined in each protocol.

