### 2.2 Secondary objective(s)

- 2.2.1 To describe the PFS of SBRT + pembrolizumab (MK-3475) compared to pembrolizumab (MK-3475) alone across RECIST measurable (including both radiated and non-radiated) cancer deposits.
- 2.2.2 To describe the overall response rate of SBRT + pembrolizumab (MK-3475) compared to pembrolizumab (MK-3475) alone in both radiated and in non-radiated deposit(s).
- 2.2.3 To determine the PFS at 6 months of SBRT + pembrolizumab (MK-3475) compared to pembrolizumab (MK-3475) alone across all cancerous deposits by RECIST.
- 2.2.4 To determine the rate of grade >3-4 adverse events, by organ system, by CTCAEv5.0.

- 2.2.5 To determine the local control of SBRT treated tumors.
- 2.2.6 To calculate delivered radiation dose using cone-beam CT images collected on the radiation treatment table in the final treatment position.

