- \*\* Physical examination, adverse event assessments, labs and scans are required  $\leq 12$  weeks after the end of treatment; thereafter, every 6 months until disease progression for a maximum of 5 years following registration or more frequently as clinically indicated. See also [Section 12.0](#). At time of progression, withdrawal or removal, only survival information should be collected every 6 months for 5 years after registration.
- \*\*\* Radiation therapy will be administered to 1 cancer deposit concurrent with the first dose or started within the first cycle of pembrolizumab (MK-3475) administration. Eligibility must have been documented prior to administration of radiation.
- † Only required if there is evidence or suspected brain mets
- # All sites of known disease as clinically indicated.
- 1 To be completed after registration and prior to treatment (See Appendix I). This questionnaire is included on all Alliance trials in order to further study the relationship between these assessments and overall survival in a meta-analysis setting.
- 2 For women of childbearing potential (see [Section 3.2](#)). Must be done  $\leq 7$  days prior to registration.
- 3 Baseline scans can include either: 1) a CT, spiral CT, or MRI or 2) an FDG-PET scan and diagnostic CT performed with both IV and oral contrast, and the CT acquired with 5 mm or less slice thickness. Supporting documentation is to be submitted, per [Section 6.1](#). Response assessment should include assessment of all sites of disease and use the same imaging method as was used at baseline.
- A After Cycle 3 (prior to cycle 4) then every 9 weeks, (prior to the start of cycles 4, 7, 10, 13, 15, etc.).

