**13.4 Supplementary Analysis Plans****13.4.1 Secondary Endpoints**

**Progression Free Survival among all RECIST lesions:** This endpoint is the same as the primary endpoint, but includes both irradiated and non-radiated lesions. It is a time to event endpoint and will be evaluated using the Kaplan- Meier method. PFS time is defined as the number of days from randomization to either evidence of disease progression or death (without evidence of progression). Median PFS times will be calculated for each arm and a cox proportional hazards model will be constructed to determine if there is a PFS benefit for patients receiving SBRT + pembrolizumab (MK-3475) compared to pembrolizumab (MK-3475) alone.

**Overall Response Rate (OS):** A patient will be declared to have responded to therapy if they have at least a PR on 2 consecutive evaluations (i.e. the response is confirmed). Response rates will be calculated and compared across treatment arms utilizing a chi-square test.

**Progression Free Survival at 6 months (PFS6):** A patient will be declared a success for this endpoint if they remain on study and progression free at 6 months. The rates of success will be calculated and compared across treatment arms utilizing a chi-square test.

**Safety/Toxicity:** Maximum grade adverse events will be summarized by treatment arm in a tabular setting. This will be done overall and for the 3 month time period from date of registration.

**Local control of SBRT treated lesion:** The protocol irradiated tumors are considered to be controlled if they have no evidence of progression. No evidence of progression is defined as CR, PR, or SD. If the protocol irradiated tumor progresses the date of progression will be recorded. Local control of the protocol-irradiated tumor will be described using the Kaplan-Meier technique.

**Delivered radiation dose using cone-beam CT images:** These radiation doses will be summarized descriptively and compared to the planned dose.

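### The toxicity summary in Section 13.4.1 has no rule for deaths coded as Grade 5 'Disease progression', so tumor deaths on or soon after treatment can be counted as high-grade toxicity

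*Combined protocol and SAP*

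**What the plan says.** Four parts of the protocol bear on this; the statistical plan is its Section 13.

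- **Coding.** Section 9.3.3: "Death due to progressive disease should be reported as Grade 5", using the term 'Disease progression' in the organ class for general disorders and administration site conditions.
- **Route into the data.** A note in Section 9.3: "All deaths on study require both routine and expedited reporting regardless of causality". The Section 9.2 table requires Grade 3 to 5 events on the main adverse event form even when attribution is unrelated or unlikely. That form "Applies to AEs occurring between registration and within 30 days of the" last treatment date, and also covers events in a Clinical Follow-Up Phase, which is not defined.
- **Later events.** The late form "Applies to AEs occurring greater than 30 days after the" last treatment date, and the table requires it only for Grade 3 to 5 events with possible, probable or definite attribution. Under Section 5.0, once a patient has progressed, withdrawn or been removed, "only survival information should be collected every 6 months for 5 years after registration".
- **Analysis.** Section 13.4.1, Safety/Toxicity: "Maximum grade adverse events will be summarized by treatment arm in a tabular setting". Two periods are planned: the whole study, and the first 3 months after registration. The section does not mention attribution, the term 'Disease progression', or whether the maximum is taken per patient, per organ class or per term. The objective it serves, 2.2.4, is "To determine the rate of grade >3-4 adverse events, by organ system, by CTCAEv5.0".

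**The concern.** The coding rule suits expedited reporting. The difficulty comes when the same record flows into a maximum-grade table that has no instruction to set it apart. A patient who dies of Merkel cell carcinoma while on pembrolizumab is then displayed at the highest toxicity grade, although the event is a failure of efficacy.

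The trial tests whether SBRT delays progression. If progression deaths differ between arms, the high-grade toxicity rates differ as well, with no difference in treatment harm. The arm that controls the tumor better looks safer, whichever arm that is. The general disorders class is the most exposed. It also holds fatigue, the only event that the pembrolizumab risk list in Section 9.4.1 places in its likely (>20%) column, so its high-grade rate would mix a common drug effect with tumor deaths.

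**Working it through.** **Step 1. Is the route open?** Section 9.3.3 assigns the grade, term and organ class. Sections 9.2 and 9.3 require the event on the routine form regardless of cause. Section 13.4.1 has no filter or exclusion. By contrast, the stopping rule in Section 13.5 is limited to events at least possibly related to treatment, so the plan states an attribution limit where it wants one. The route is open.

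**Step 2. Which deaths travel it?** Mainly those on treatment or within 30 days of the last dose. Section 12.1.2 lets clinically well patients continue after RECIST progression if confirmed progression under the immune criteria is not met, so some progression deaths can fall in this window. After it, the late form takes only related events, and after progression only survival is collected. The undefined Clinical Follow-Up Phase leaves the upper limit unclear.

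**Step 3. Size.** The plan states no adverse event rate or progression-death rate, so there is no figure to reproduce. Inputs:

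- n = 48 per arm (Section 13.2.2).
- t = share of patients with a true grade 3-4 event. Assumed 20% in both arms.
- q = share with a progression death captured as Grade 5. Assumed 5-10% in Arm 1 and 3-7% in Arm 2, as if SBRT works.
- Toxicity and progression death are assumed independent.

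Formulas, if one overall maximum grade per patient is tabulated:

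- share shown at grade 3 or higher = t + q(1 − t)
- share shown with maximum grade 3-4 = t(1 − q)
- patients whose grade 3-4 event is hidden = n × t × q

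| | q | Grade ≥3 shown | Maximum grade 3-4 shown | Patients masked |
|---|---|---|---|---|
| Arm 1, low | 5% | 0.20 + 0.05 × 0.80 = 24.0% | 19.0% | 0.48 |
| Arm 1, high | 10% | 0.20 + 0.10 × 0.80 = 28.0% | 18.0% | 0.96 |
| Arm 2, low | 3% | 0.20 + 0.03 × 0.80 = 22.4% | 19.4% | 0.29 |
| Arm 2, high | 7% | 0.20 + 0.07 × 0.80 = 25.6% | 18.6% | 0.67 |

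Against a true 20% in each arm, the rate is inflated by 4 to 8 points in Arm 1 and by 2.4 to 5.6 points in Arm 2. Pairing low with low and high with high, the spurious difference is 24.0 − 22.4 = 1.6 to 28.0 − 25.6 = 2.4 points, or about one patient in 48. If q is equal in the two arms, both rates are inflated equally and no difference arises.

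Over a wider grid (t = 10-30%, q = 2-15%), the share shown at grade 3 or higher runs from 11.8% (t = 10%, q = 2%) to 40.5% (t = 30%, q = 15%). Masking runs from 0.1 to 2.2 patients per arm.

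**Step 4. How layout changes this.** Masking across all toxicity needs a single maximum per patient. In a table by organ class, Grade 5 'Disease progression' can hide only a grade 3-4 event in the general disorders class; colitis, pneumonitis and hepatic events are untouched. In a table by term it hides nothing. Inflation of the general disorders rate remains: with no other high-grade event in that class, the class would still show q, that is 5-10% versus 3-7%.

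**The case against.** The best case on the other side is that this is a small wording gap. Section 13.4.1 is a descriptive summary with no between-arm test. Section 9.0 requires an attribution for each adverse event, and these deaths carry their own term, so an analyst can separate them at reporting. An all-cause table is a defensible default. The stopping rule in 13.5 is unaffected where such deaths are attributed as unrelated or unlikely. All of this stands, and it limits the weight of the point. It does not close the gap, because nothing in the plan tells the analyst to make the separation.

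A reader might infer three stronger things, which the documents do not support.

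- **That the plan tabulates one maximum per patient, irrespective of cause.** Section 13.4.1 says neither; both are read from its silence. Objective 2.2.4 is by organ class, which points to a different layout.
- **That grade 3-4 toxicity is hidden in general.** Masking depends on layout, as Step 4 shows. The objective's grade range is also unclear. If Grade 5 counts, the rate is inflated. If it does not, these deaths do not enter the rate directly, but a maximum-grade table can still lose a grade 3-4 event.
- **That every progression death up to the data cut becomes a Grade 5 toxicity.** Section 9.3's reference to deaths on study could be read that way. Against it, the late form takes only related events, Section 9.3.3 requires expedited reporting of deaths more than 30 days after the last dose only when they are at least possibly related, and Section 5.0 limits collection after progression to survival. The undefined terms make the window uncertain, but that does not justify sizing the problem on all deaths.

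**Conclusion.** The point holds in a limited form. As written, Section 13.4.1 allows progression deaths on treatment or within about 30 days of the last dose, and possibly somewhat later, to be counted as Grade 5 toxicity. The main effect is inflation of the grade 3-or-higher rate and of the general disorders rate, by an amount that depends on how many patients die of tumor in each arm. Masking of earlier grade 3-4 events is secondary and depends on layout.

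The size, about 24-28% versus 22-26% against a true 20%, with at most about one patient per arm masked, rests wholly on assumed toxicity and death rates and on independence. The lower Arm 2 death rate is also an assumption, since the protocol's design effect is for PFS and no survival effect is stated. No efficacy decision depends on this. It is worth correcting before analysis because the distortion can differ by arm and the remedy is cheap.

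**What to change.** In Section 13.4.1 (Safety/Toxicity), and for the organ-class rates under objective 2.2.4, state that:

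1. Grade 5 'Disease progression' is excluded from the maximum-grade tables, so that each patient's worst other adverse event is shown.
2. Maximum grade is tabulated by term and by organ class, once for all-cause events and once for events at least possibly related to treatment.
3. All deaths are reported in a separate table by arm and cause (progression, treatment-related, other), so that no death is lost from view.

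Leave the reporting rule in Section 9.3.3 unchanged.

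The cost is a few sentences of analysis text and one or two extra tables. Term, grade and attribution are already collected, so no new data are needed.
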